## **7.6. Baseline Values**

Baseline values are the values obtained at Visit 1, 0 Hour (Time 0 min), prior to any treatment administration. If the Visit 1, 0 Hour assessments are missing, any value collected prior to treatment administration will be treated as the baseline.

## **8. SUMMARY OF STUDY DATA**

### **8.1. Subject Disposition**

A summary of the analysis sets includes the number and percentage of subjects by Stage 1 treatment group and overall for the following categories: subjects in the ARP, subjects in the SP, subjects in the mITT Population, and subjects in the PP Population. All percentages will be based on the number of subjects in the ARP. A similar summary will be presented by Stage 2 treatment group.

End of trial information will also be summarized in these tables, including the number of subjects completing the study, the number of subjects who prematurely discontinued the study with reasons for withdrawal, the number of subjects completing the study medication dosing, and the number of subjects who prematurely discontinued the study medication with reasons for study medication discontinuation.

A by-subject data listing of study completion information including the reason for premature study withdrawal, if applicable, will be presented.

### **8.2. Protocol Deviations**

Major protocol deviations, as determined by a Sponsor blinded review of the data prior to database lock and unblinding of the study, may result in the removal of a subject's data from the PP Population. The Sponsor or designee will be responsible for producing the final deviation file; this file will include a description of the protocol deviation and clearly identify whether this violation warrants exclusion from the PP Population. This file will be finalized prior to database lock.

All protocol deviations will be presented in a by-subject data listing, with a flag to indicate if a deviation was considered major and/or exclusionary.

### **8.3. Demographics and Baseline Characteristics**

Subject demographic data and baseline characteristics will be tabulated and summarized descriptively by Stage 1 treatment group, Stage 2 treatment group, and overall. The demographic data and baseline characteristics will be summarized for the mITT Population, PP Population, SP, and ARP. If the mITT population is equivalent to any of the other populations, then only the mITT version will be generated rather than repeating equivalent summaries.

The demographics consist of age (year), sex, race, ethnicity, and study eye, iris type (light, dark). A subject's age in years is calculated using the date of the informed consent and date of birth. Age will be summarized using descriptive statistics. The number and percentage of subjects by sex, race, ethnicity, study eye, and iris type will also be reported. Percentages will be based on the total number of subjects in the study population presentation.

The following baseline characteristics will be summarized for study eye, fellow eye, and binocular (if applicable), using descriptive statistics:

- BCDVA (photopic and mesopic)
- DCNVA (photopic and mesopic)
- DCIVA (photopic)
- Pupil diameter (photopic and mesopic)
- IOP

All demographic and baseline information will be presented in by-subject listings.

#### **8.4. Medical History**

The number and percent of subjects with individual medical histories will be summarized for all subjects by Stage 1 treatment group, Stage 2 treatment group, and overall. Non-ocular and ocular medical history will be summarized separately.

Medical history will be coded using the MedDRA Version 25.1. The number and percentage of subjects with any medical history will be summarized overall and for each system organ class (SOC) and preferred term (PT). Percentages will be calculated based on number of subjects in the SP.

Subject medical history data including specific details will be presented in by-subject listings.

#### **8.5. Prior and Concomitant Medications**

The number and percentages of all concomitant medications will be summarized by Stage 1 treatment group, Anatomical Therapeutic Chemical (ATC) level 4, and PT. The total number of concomitant medications and the number and percentages of subjects with at least 1 concomitant medication will be summarized by Stage 1 treatment group. A similar summary will be presented by Stage 2 treatment group. All summaries will be performed using the SP.

A concomitant medication is defined as any medication taken on or after the day of first exposure to study drug.

Prior medications are defined as any medication that has a start and stop date prior to the day of first exposure to any study drug, collected from up to 30 days prior to Screening. The total number of prior medications and the number and percentages of subjects with at least 1 prior medication will be summarized by Stage 1 treatment group, Stage 2 treatment group, and overall.

### 8.6. Treatment Exposure and Compliance

Exposure to Treatment 1 for the evening of Stage 1 Day 2 through the evening prior to Visit 2 (Stage 1 Day 8) will be [REDACTED]

For Stage 2, exposure to Treatment 1 will be assessed [REDACTED]

## 9. EFFICACY ANALYSES

Unless otherwise noted, efficacy will be assessed using the mITT and PP populations, with subjects included in their randomized treatment regardless of the treatment they actually received. For the analysis of the primary efficacy endpoint, imputation will be performed for missing data as described in Section 7.3.2.3. Confirmatory analysis of the primary efficacy endpoint may be performed using the ARP, if different from the mITT, also using imputation for missing data.

All efficacy assessment data, regardless of whether they are included in the analysis, will be presented in by-subject listings.

### 9.1. Clinical Efficacy

All efficacy data will be summarized by treatment group for the Baseline assessment; for Visit 1 (Stage 1 Day 1) post-treatment time points (0.5 hours, 1 hour, 3 hours, 5 hours, and 8 hours); Visit 2 (Stage 1 Day 8) time points (12 hour post-Treatment 1 dose, 12.5 hours, 13 hour, 15 hours, 17 hours, and 20 hours); Visit 3 (Stage 1 Day 10); Visit 4 (Stage 2 Day 1) time points (12 hour post-Treatment 1 dose, 0.5 hours, 1 hour, 3 hours, 5 hours, and 8 hours post-Treatment 2); and Visit 5 (Stage 2 Day 8) time points (12 hour post-Treatment 1 dose, 0.5 hours, 1 hour, 3 hours, 5 hours, and 8 hours post-Treatment 2).

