Subjects will restart dosing daily with Treatment 1 in the evening immediately prior to Visit 4 (Stage 2 Day 1) as close to 12 hours prior to the scheduled time for Visit 4 for the 12-hour assessments. At this visit, after completion of the 12-hour assessments for Treatment 1, subjects will be administered their morning dose of Treatment 2 (at Time 0 min) at the study site, and efficacy and safety measurements will be made at multiple post-dose timepoints over the next 8 hours. During Stage 2, subjects will administer Treatment 1 in the evenings near bedtime and Treatment 2 in the mornings from the evening prior to Visit 4 (Stage 2 Day 1) for the next 7 days or until the evening before their scheduled Visit 5 (Stage 2 Day 8). On the evening prior to Visit 5, Treatment 1 should be administered as close to 12 hours prior to the scheduled time for Visit 5. At Visit 5, measurements will be made before dosing with Treatment 2 at Time 0 min and at multiple post-dose timepoints over 8 hours after dosing with Treatment 2.

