Table 2. Schedule of Events for Stage	Visit 4[a]							Visit	5[a]					
	Stage 2 Day 1 (Day 15 to 22)						Stage 2 Day 8 (7 days after Stage 2 Day 1)							
Time (hr)[b]	12 hr post Treatment 1	0	0.5	1	3	5	8	12 hr post Treatment 1	0	0.5	1	3	5	8
Prior/Concomitant medications	Х							X						
Urine pregnancy test[c]	Х							Х						
HR/BP														Х
Biomicroscopy														Х
IOP[g]														Х
Ophthalmoscopy[h]														Х
AEs	Х													Х
Subject questionnaire[k]					Х							Х		
In-office Treatment 2: LDP or LDP vehicle[i]		Х							Х					
Ocular tolerability[j]		Х							Х					
Treatment 1: Nyxol or placebo and Subject							X							Х
diary dispensed / reviewed[1]							Λ							Λ
Treatment 2: LDP or LDP vehicle and Subject diary dispensed / collected[i]							X							Х

AE, adverse event; BCDVA, best-corrected distance visual acuity; BP, blood pressure; DCNVA, distance-corrected near visual acuity; HR, heart rate; ID, identification; IOP, intraocular pressure; LDP, Low-Dose Pilocarpine; OD, right eye; OS, left eye; PD, pupil diameter; VA, visual acuity.

[a] Time of visits will be scheduled relative to the prior evening's dose of Treatment 1. Visits 4 and 5 will be scheduled such that the 12 hour post-dose assessments on Visits 4 and 5 will occur approximately 12 hours ( $\pm$  1 hour) after the prior evening's dose of Treatment 1.

[b] An additional  $\pm 5$  min is permitted for measurements at 0.5 and 1 hour; an additional  $\pm 10$  min is permitted at 3, 5, and 8 hours for Visits 4 and 5.

[c] Urine pregnancy test is for females of childbearing potential only.

[g] IOP performed with Tono-Pen or Goldmann applanation tonometry.

[h] Direct or indirect ophthalmoscopy performed without dilation. Use of 90 D lens (indirect) is allowed.

[i] Treatment 2: One drop of LDP or LDP vehicle in each eye dosed daily in the mornings beginning on the day after Visit 4 and daily through the day prior to Visit 5. At Visits 4 and 5, subject will be dosed with Treatment 2 at the study site. Subject will bring Treatment 2 kit and diary to Visits 4 and 5 for review and accountability.

[j] Ocular tolerability performed it will be assessed at the beginning of each specified timepoint after dosing at Visits 4 and 5.

[k] Subject questionnaire (Appendix 5 and Appendix 6) will be completed by the subject at specified visits and timepoints.

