#### 7.1. Treatment Adherence

Following the completion of Visit 1 (Stage 1 Day 1), subjects will be dispensed Treatment 1 study drug for dosing at home in the evenings and a Treatment 1 subject diary to document dosing.

At the end of Visit 4 (Stage 2 Day 1), subjects will be dispensed Treatment 2 study drug for dosing at home in the mornings and a Treatment 2 subject diary to document dosing.

Subjects must bring their used and unused study medications and subject diaries with them to Visit 2 (Stage 1 Day 8), Visit 4 (Stage 2 Day 1), and Visit 5 (Stage 2 Day 8).

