#### *Stage 1: Dosing of Treatment 1*

Individuals who are potential subjects are identified by the study center to schedule the Screening Visit. If a subject successfully completes their Screening Assessments, then Visit 1 becomes the Baseline Visit.

Once a subject arrives at the study center, a member of the Site Staff interviews the individual as to their qualifications for participation in the study, and if the subject wishes to continue, the informed consent form (ICF) is signed, and a subject number is assigned.

If all eligibility criteria are met, the subject is randomized into the study.

At Visit 1 (Stage 1 Day 1), eligible subjects were randomized, and the first dose of Treatment 1 was administered at the study site at Time 0 min (note: if Visit 1 is split into 2 separate days, then dosing occurs on the second day). Efficacy and safety measurements were made before dosing with Treatment 1 (Time 0 min) and at multiple post-dose timepoints from 30 min to 8 hours.

In Stage 1, the safety and efficacy of Nyxol as a single agent was evaluated after 1 day and 7 days of daily dosing.

Following Visit 2 (Stage 1 Day 8), subjects discontinued dosing Treatment 1 for 7 to 14 days (Washout Period). During the Washout Period, subjects returned for Visit 3 (Stage 1 Day 10  $\pm$  1 day) to assess the resolution of drug treatment effects.

During Stage 1, Treatment 1 is dosed daily in the evenings near bedtime starting with the day after completion of Visit 1, except for Visit 1 [Stage 1 Day 1], when the subject is dosed during the day at the study site, and the evening before Visit 2, when Treatment 1 is dosed as close to 12 hours prior to Time 0 min at Visit 2.

Analysis will consist of comparison across the 2 arms:

- Nyxol
- Placebo

*Stage 2: Dosing of Treatments 1 and 2*

Visit 4 (Stage 2 Day 1) is the start of Stage 2. In Stage 2, the efficacy and safety of Nyxol + LDP was evaluated following 1 day and 7 days of dosing, in which Treatment 1 (Nyxol or placebo) is dosed daily in the evenings near bedtime, except the evening before Visits 4 and 5, when Treatment 1 is dosed as close to 12 hours prior to the scheduled time for those visits. Treatment 2 (LDP or LDP vehicle) is dosed daily in the mornings. Treatment 2 will be dosed at the study site at the beginning of Visits 4 and 5 (Stage 2 Days 1 and 8, respectively).

Analysis consists of comparison across the 4 arms:

- Nyxol + LDP
- Nyxol + LDP vehicle
- Placebo + LDP
- Placebo + LDP vehicle

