## **7.4. Planned Study Analyses**

### **7.4.1. Statistical Summaries: Descriptive and Inferential**

Categories for data presentation and analysis will consist of each treatment group: Nyxol and placebo for Stage 1, and Nyxol + LDP, Nyxol + LDP vehicle, Placebo + LDP, and Placebo + LDP vehicle for Stage 2.

All statistical tests will be two-sided and a difference resulting in a p-value of less than or equal to 0.05 will be considered statistically significant. The p-values for the analysis of secondary efficacy endpoints and safety endpoints will be considered descriptive, unless the endpoint is used for the hierarchical testing method. All p-values will be rounded to and displayed in four decimals. If a p-value less than 0.0001 occurs, it will be shown in tables as <0.0001.

Descriptive summaries of variables will be provided where appropriate. For continuous variables, the number of non-missing values (n), mean, standard deviation, median, minimum, and maximum will be tabulated by treatment group. For categorical variables, the counts and proportions of each value will be tabulated by treatment group. Expansion of descriptive table categories within each treatment may occur if such elaborations are thought to be useful.

All study-related data collected will be presented in listings. Study-related data not subject to analysis according to this plan will not appear in any tables or graphs but will be included in the data listings.

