**Table 3 Snellen Equivalents to VA Assessment Letters Read**

DCNVA/DCIVA letters	Snellen	BCDVA letters
≥75	20/15	≥60
70 - 74	20/20	55 - 59
65 - 69	20/25	50 - 54
60 - 64	20/32	45 - 49
55 - 59	20/40	40 - 44
50 - 54	20/50	35 - 39
45 - 49	20/63	30 - 34
40 - 44	20/80	25 - 29
35 - 39	20/100	20 - 24
30 - 34	20/125	15 - 19
25 - 29	20/160	10 - 14
<25	20/200	<10

Each of the continuous secondary efficacy endpoints will be analyzed using analysis of covariance (ANCOVA), with observed value as the dependent variable, treatment, [REDACTED] respective baseline value included as the covariate. Another ANCOVA will be applied with change from baseline as the dependent variable using the same factors and covariates.

The output from each ANCOVA will include the LSM and SE for all treatment groups, along with each LSM, the 95% CI and associated p-value for Nyxol vs. Placebo for Stage 1 time points, and Nyxol + LDP vs. Nyxol + LDP vehicle, Placebo + LDP, and Placebo + LDP vehicle for Stage 2 time points. [REDACTED]

For each of the secondary endpoints related to percent of subjects achieving certain criteria, the analysis will be performed using a logistic regression model with treatment and light/dark irides as factors, and the respective baseline as a covariate. For each analysis, the percentage

of subjects in each treatment group meeting the criteria will be presented, and the OR with 95% CI and p-value will be provided for Nyxol vs. Placebo for Stage 1 time points, and Nyxol + LDP vs. Nyxol + LDP vehicle, Placebo + LDP, and Placebo + LDP vehicle for Stage 2 time points. Categorical pupil diameter endpoints will be assessed using the study eye, fellow eye, and either eye, which is defined as achieving a given criterion in either eye.

In addition, each secondary efficacy endpoint will be [REDACTED].

Finally, select questions from the Subject Questionnaire will be analyzed. The results for Question 1 (change in near vision) and Question 5 (satisfaction with near vision) will be analyzed at Visit 2 (Stage 1 Day 8) and Visit 5 (Stage 2 Day 8) using an ANCOVA model with numeric observed response as the dependent variable ([REDACTED] and treatment as a factor. Only observed subject questionnaire data will be used; no imputation will be performed for missing data.

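### At the Visit 4 12-hour assessment, before any Treatment 2 dose, the SAP's readable text calls for four-arm contrasts where Nyxol versus placebo could be pooled

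*SAP*

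**What the plan says.** **Order of dosing at Visit 4.** Subjects restart Treatment 1 on the evening before the visit. Protocol 3.5 then states that "after completion of the 12-hour assessments for Treatment 1, subjects will be administered their morning dose of Treatment 2 (at Time 0 min"), and Protocol 5.4.4 gives the same order. Home supplies come later still: "At the end of Visit 4 (Stage 2 Day 1), subjects will be dispensed Treatment 2 study drug" (Protocol 7.1), with home doses "dosed daily in the mornings beginning on the day after Visit 4" (Protocol Table 2, note [i]).

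**Stage and time points.** SAP 5.1 states that "Visit 4 (Stage 2 Day 1) is the start of Stage 2". SAP 9.1 lists "Visit 4 (Stage 2 Day 1) time points (12 hour post-Treatment 1 dose" first among that visit's efficacy time points, ahead of those timed from Treatment 2.

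**Groups and contrasts.** SAP 7.4.1 defines the groups by stage: "Nyxol and placebo for Stage 1, and Nyxol + LDP, Nyxol + LDP vehicle, Placebo + LDP, and Placebo + LDP vehicle for Stage 2". SAP 9.1.2 specifies Nyxol versus placebo for Stage 1 time points and "Nyxol + LDP vs. Nyxol + LDP vehicle, Placebo + LDP, and Placebo + LDP vehicle for Stage 2 time points". It says this for both the ANCOVA and the logistic regression of secondary endpoints. The readable text of 9.1.2 does not mention the assessment made before Treatment 2.

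**Status of the tests.** Under SAP 7.4.1, secondary p-values are descriptive unless the endpoint belongs to the testing hierarchy.

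**The concern.** The grouping rule follows the stage label, not what subjects have received. At the Visit 4 12-hour assessment only Treatment 1 distinguishes the groups, so the design offers a two-group comparison there, as in Stage 1. Splitting by a Treatment 2 assignment that has not yet taken effect produces one contrast with nothing to estimate and two smaller, overlapping versions of the same contrast.

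The time point has some interest of its own. It follows a 7- to 14-day washout and a single restart dose, so it is the study's only 12-hour measurement after one evening dose of Nyxol. Visit 1 is dosed in the daytime and followed to 8 hours, and Visit 2 follows about a week of dosing. What is at stake is the precision of that estimate and the clarity of the output, not the validity of the trial's main conclusion.

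**Working it through.** **1. Group sizes.** Inputs: about 320 randomized 1:1:1:1 (SAP 5.1); 300 evaluable, 150 per Treatment 1 arm (Protocol synopsis, sample size justification).
- Four arms: 320/4 = 80 per group. By Treatment 1: 320/2 = 160 per group. Both match SAP 5.1.
- Evaluable: 300/4 = 75 and 300/2 = 150. Dropout allowance: 300 + 20 = 320, as stated.

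The planned power and assumed rates are blacked out, so the sample size itself cannot be re-derived.

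**2. What each planned contrast compares at Visit 4, 12 hours.**

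| Contrast in SAP 9.1.2 | Treatments actually received by then | Subjects |
|---|---|---|
| Nyxol + LDP vs Nyxol + LDP vehicle | Nyxol vs Nyxol | about 80 vs 80 |
| Nyxol + LDP vs placebo + LDP | Nyxol vs placebo | about 80 vs 80 |
| Nyxol + LDP vs placebo + LDP vehicle | Nyxol vs placebo | about 80 vs 80 |

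In the first row the null hypothesis is true by design, so a significant result can only be chance. A simulation of the unadjusted two-proportion test, with 75 per group and both rates at 30.1%, rejected 4.9% of the time. The second and third rows share the same Nyxol arm. The Nyxol + LDP vehicle subjects are never compared with placebo.

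**3. Loss of precision.** With equal groups of size n, the standard error of a difference is proportional to sqrt(2/n).
- Ratio, four-arm to pooled: sqrt(2/75) / sqrt(2/150) = sqrt(2) = 1.41. The ratio at 80 and 160 is the same.
- Interval narrowing from pooling: 1 − 1/1.41 = 29%.

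This does not depend on any assumed response rate. A single four-arm model would use all subjects to estimate residual variance, but each contrast would still rest on two groups of about 80.

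**4. Illustration.** Protocol 3.2 gives Phase 2 12-hour responder rates of 30.1% (Nyxol) and 13.5% (placebo).
- Half-width = 1.96 × sqrt[(0.301 × 0.699 + 0.135 × 0.865)/n] = 1.96 × sqrt(0.3272/n).

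| Basis | Four-arm contrast | Pooled contrast |
|---|---|---|
| Evaluable, n = 75 vs 150 per group | 12.9 points | 9.2 points |
| Randomized, n = 80 vs 160 per group | 12.5 points | 8.9 points |

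These rates follow 3 to 4 days of dosing, not one dose, and omit the condition of fewer than 5 letters lost in BCDVA. The widths are for a risk difference, whereas the SAP reports odds ratios and least-squares means. They show scale only.

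**5. Scope.** By the Visit 5 12-hour assessment subjects have had Treatment 2 daily since Visit 4, so the four arms differ in treatment received and the argument does not apply. One loose end: Protocol Table 2, note [i] has subjects bring a Treatment 2 kit to Visit 4, while Protocol 7.1 dispenses it at the end of that visit. The two should be reconciled, but the stated order of the first Treatment 2 dose is unaffected.

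**The case against.** **The deciding text may be redacted.** SAP 9.1 by itself speaks only of summaries by treatment group. The contrasts come from 9.1.2, which defers details to a table list that is blacked out, and a redaction directly follows the ANCOVA contrasts. The endpoint list in SAP 4.2.2 is also hidden. This stands: a reader might infer that the SAP definitely tests four arms here, but the documents show only that the readable rule does so and states no exception.

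**Labelling.** A reader might call it an error to report results under Nyxol + LDP before any LDP was given. The documents do not support that. Efficacy arms are labelled by randomized assignment, made before Stage 1, and SAP 9.1 names this time point by Treatment 1, apart from those timed from Treatment 2.

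**The four-arm display is useful.** It gives each arm's level just before Treatment 2 and shows whether the arms were comparable after washout. This stands, and removing the display would be a real loss.

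**Power is a poor yardstick.** At the Phase 2 rates, power would be 69.6% with 75 per group and 94.0% with 150. Those figures move widely with the assumed rates: 25% vs 13.5% gives 43% and 72%, 35% vs 13.5% gives 88% and 99%, and 30.1% vs 20% gives 30% and 52%. The tests also appear to be descriptive. A claim that the trial is underpowered here is not supported.

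**Nyxol alone is analyzed elsewhere with about 160 per group**, at Visits 1 and 2, and SAP 3.2 permits additional analyses. This is true and limits the importance of the point. Neither visit gives a 12-hour value after one evening dose, however, and a prespecified comparison is preferable to one added later.

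**Conclusion.** The point holds as a modest, nearly free improvement. On the readable text, the SAP applies four-arm contrasts at an assessment that precedes Treatment 2. One contrast is uninformative, and the other two estimate Nyxol versus placebo with a standard error 1.41 times that of the pooled comparison.

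Randomization is intact, so none of the contrasts is biased. The primary endpoint and the comparisons named in SAP 7.5 are all at Visit 5, 30 minutes, and are unaffected. A reader might infer a threat to the confirmatory results; the documents do not support one, although the full hierarchy in SAP 12.3 is blacked out.

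The conclusion rests on equal allocation, on the dosing order in Protocol 3.5 and 5.4.4, and on there being no exception in the redacted text. The 29% narrowing depends only on group sizes; the half-widths in percentage points depend on borrowed Phase 2 rates.

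**What to change.** First check the redacted table list and the redacted text in SAP 9.1.2 for an existing exception. If there is none, add to 9.1.2 before unmasking:

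- At the Visit 4 12-hour post-Treatment 1 time point, the inferential comparison is Nyxol versus placebo, pooled over Treatment 2 assignment, with the same model as for Stage 1.
- Four-arm contrasts begin at 0.5 hours post-Treatment 2 at Visit 4.
- The four-arm descriptive summary at the Visit 4 12-hour time point is kept as the reference before Treatment 2.
- The Visit 5 12-hour time point keeps its four-arm contrasts.

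The cost is this wording and the affected table shells. No new data are needed. The one drawback is that the inferential grouping changes between 12 hours and 0.5 hours within Visit 4; keeping the arm-level display and adding a table footnote deals with that.
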